9.11.5 Analysis of Exploratory Endpoints

Exploratory endpoints will be analyzed and summarized using the FAS unless otherwise indicated. The exploratory endpoints will be assessed using descriptive summaries. However, if deemed of interest following review of the summaries, further analyses of these endpoints may be conducted and will be considered post-hoc. None of the exploratory endpoint analyses will be adjusted for multiplicity.

9.11.5.1 Proportion of Subjects Reporting Day 28 Cure Rates

For FAS subjects, summary statistics for the exploratory endpoints listed below by randomized treatment group and overall will be provided. The definitions of each of the variations of cure endpoint are provided in Section 6.3. There will be no adjustment for region:

- Complete Cure, (n, % FAS)
- Clinical Cure, (n, % FAS)
- Microscopic or Dermatoscopic Cure, (n, % FAS)
- Complete Cure without regard to pruritus (n, % FAS)
- Investigator Assessed Cure:
 - The scabies infestation is clear with all signs resolved, (n, % FAS)
 - The scabies infestation is clear with incomplete resolution of signs, and no additional treatment with standard of care is warranted, (n, % FAS)
 - The scabies infestation is not clear and additional treatment with standard of care is warranted, (n, % FAS)

Along with the number and percent (proportion), the 95% CIs intervals for each treatment group and overall will also be provided. For each of the endpoints, the missing data and imputation methods are outlined under Section 6.3. In general, no imputation will be conducted except for subjects exposed to scabicides. The analysis will be conducted using the FAS.

Additionally, the table will be repeated with stratification by region, summarized by randomized treatment group and overall.

9.11.5.2 Concordance Between Complete Cure and Investigator Assessed Cure

The number and percent of subjects with concordant outcomes for the Complete Clinical Cure and Investigator Assessed Cure, as defined in Section 6.3, will be presented by randomized treatment group and overall. For each group and overall, there will be two concordant and two discordant outcome pairs, each pair corresponding to a cell in a 2x2 table. The results for each of the four outcome pairs will be provided. The Kappa statistic, a measure of agreement corrected for chance agreement, and its p-value, will also be calculated.

The analysis will be conducted using only FAS subjects with non-missing data.

9.11.5.3 Change From Baseline in Lesion Counts

Aggregate summary statistics for lesion counts will be provided by randomized treatment and overall using the FAS. For this analysis, descriptive statistics will be provided for the Baseline count, the Day 28 count, the change from Baseline difference and percent change from Baseline. Summary statistics will include the means, medians, SDs, minimums and maximum values and the number of non-missing FAS subjects in each calculation. The analysis will consist of observed data only with no imputation; however, subjects who used scabicides prior to their Day 28 visit will have their Day 0 value carried forward.

9.11.5.4 The Proportion of Subjects with Secondary Bacterial Skin Infections at Day 28

This analysis will present the number and percent (proportion) of index FAS subjects with secondary bacterial skin infections at Day 28. Only FAS subjects with observed data will be included in the analysis. There will be no imputation, and subjects receiving scabicides will be excluded from the analysis.

9.11.5.5 Plasma Concentrations of Moxidectin

Listings of individual moxidectin concentration versus time data by treatment group for each of the four collection timepoints will be provided for the Pharmacokinetic Analysis Set, showing any below the limit of quantification (BQL) and missing samples. Aggregate summary statistics for moxidectin concentration versus time data by dose for each of the four collection timepoints will be reported in tabular format. The number of observations, number of observations BQL, arithmetic mean (referred to as mean), median, SD, coefficient of variation (CV), minimum, maximum, geometric mean, geometric SD and geometric CV will be provided.

Individual moxidectin concentration data will also be used for population-PK and PK/pharmacodynamic analyses, which are outside the scope of this SAP. Further details pertaining to these analyses are outlined in separate MSAPs and the outcomes of the analyses will be reported separately.

9.11.6 Subgroup Analyses

Descriptive summaries for the primary efficacy endpoint (unadjusted for region) will also be provided for the following subgroups:

- Region
- Age (18 to 64 and ≥ 65)
- Gender
- Race
- Ethnicity
- Method of parasitological assessment at Baseline (microscopy or dermoscopy)
- Scabies Severity:
 - Mild (≤ 10 lesions)
 - Moderate (11 to 49 lesions)
 - Severe (≥ 50 lesions)
- Clinical Site (US sites that enroll less than 5 subjects will be pooled)

9.11.7 Extent and Pattern of Missing Data

The extent and pattern of missing data will focus on the primary efficacy endpoint, Complete Cure at Day 28. The number and percent of FAS subjects with imputed values for this endpoint will be provided by randomized treatment group and overall as well as by region. In addition to the endpoint, the number and percent of subjects missing each of the components from which the endpoint is derived will also be presented. A summary of the number and percent of subjects missing the Complete Cure primary endpoint due to a missed visit or one or more missing endpoint components will also be summarized.

9.12 Safety Analysis

The analysis of safety will include TEAEs, vital signs, physical exams, clinical laboratory assessments using the SfAS. The analysis of safety will be descriptive; however, statistical models and/or hypothesis testing may be conducted if determined to be helpful in the

interpretation of the results. All post hoc safety analyses will be identified as such. Summary data will be provided for each treatment cohort and overall. No safety data will be imputed.

It is anticipated that the overwhelming majority of participants will receive their planned dose of study drug; however, it is possible that dosing errors may result in some participants receiving the wrong study drug dose. Should this occur, a summary of the number and percent of participants with dosing errors resulting in the receipt of the incorrect study drug dose will be provided.

If multiple measurements within a time interval were taken, the last value taken within that time interval will be used. If the last value within the time interval cannot be determined, the worst value within the time interval will be used. All recorded values, including repeated measurements, will be included in listings. Values out of the normal range for the site will be flagged in the listings.

For participants in the SfAS, events occurring after signing of informed consent/assent but prior to the first exposure to study drug (i.e. non-TEAEs) will be provided in line listings only.

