1 INTRODUCTION

1.1 Background

Protocol MDGH-MOX-2002 is a Phase 2, multi-center, placebo-controlled, double-blind, randomized dose ranging study to evaluate the efficacy and safety of orally administered moxidectin in adults with scabies.

This Statistical Analysis Plan (SAP) specifies the planned analyses designed to address the study objectives outlined in clinical study protocol MDGH-MOX-2002 version 3 (including amendments 1 and 2), dated 28 Dec 2023. Where there are discrepancies, this SAP will supersede the statistical methods described in the protocol. This SAP will be finalized prior to unblinding study data for the Day 42 analysis. If the finalized SAP is amended prior to unblinding, amendments will be tracked, documented and a rationale provided for each new version. Deviations/changes from the planned analyses described in this SAP will be identified, with justification, in the appropriate section of the clinical study report. Any analysis performed not prospectively defined in this document will be labeled as post hoc and exploratory.

For further information on study conduct, the reader of this SAP is advised to refer to the protocol and other related documents. The specifications for the Tables, Figures and Listings (TFLs) described in this SAP will be provided in a separate document.

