3 STUDY OBJECTIVES

3.1 Primary Objectives

The primary objectives of the study are:

- To compare the efficacy of a single oral administration of moxidectin for each of the three moxidectin doses to matching placebo with respect to the Day 28 Complete Cure rate.
- To compare the safety of a single oral administration of moxidectin for each of the three moxidectin doses with placebo.

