6.4 Safety Endpoints

- Incidence and severity of treatment emergent adverse events (TEAEs).
- Incidence of serious TEAEs.
- Incidence of TEAEs leading to study withdrawal and/or death.
- Incidence of TEAE attribution of relatedness to study drug.
- Changes from Baseline in 12-lead electrocardiograms (ECGs), laboratory assessments and vital signs.

Unless otherwise noted incidence refers to subject incidence.

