9 STATISTICAL METHODS OF ANALYSIS

9.1 General Analytic and Reporting Principles

The results of the statistical analyses will be reported using summary tables and figures, with all data reported as listings. All analyses will be performed using SAS Version 9.4 or later.

Data will be summarized in tabular form by dose group in order of ascending dose (moxidectin 8 mg, moxidectin 16 mg, moxidectin 32 mg), placebo and overall subjects.

Summary statistics for continuous variables will consist of the number of non-missing observations (n), mean, standard deviation (SD), minimum, median and maximum, unless specified otherwise. Summary statistics for categorical variables will include the number (count) and percentage of subjects. In general, the percents will be calculated using the denominators for each treatment group within the analysis population being considered. Percentages based on other denominators will be noted. If relevant, tabulations of categorical data will include all categories captured on the eCRF even if no observations in the database appear in those categories. In this situation a '0' will be inserted. For certain categorical variables the number of participants with missing data may also be provided; however, the number missing will not be included in the calculations of percentages.

For proportions, asymptotic Wald confidence intervals (CIs) will be calculated. When the normal approximation may not hold, exact CIs may also be calculated. Confidence intervals based on bootstrapped standard errors (SEs) will be flagged in tables if relevant.

No preliminary rounding will be performed. Any rounding will only occur after analysis for the purposes of data presentation.

For any analyses using a randomized component such as bootstrapped statistics or permutation tests, the randomization seeds used to produce the analysis will be saved and documented to enable the results to be reproducible.

9.1.1 Final Efficacy Analysis at Day 42

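### Comparing each dose's safety with placebo is a primary objective, but the SAP pre-specifies no dose-versus-placebo safety estimate with an interval and names no all-moxidectin group

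*SAP*

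**What the plan says.** SAP 3.1 and protocol 6.1.1 list two primary objectives. The second is: "To compare the safety of a single oral administration of moxidectin for each of the three moxidectin doses with placebo".

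The analysis section is looser. SAP 9.12 states: "The analysis of safety will be descriptive; however, statistical models and/or hypothesis testing may be conducted if determined to be helpful". It adds: "Summary data will be provided for each treatment cohort and overall". SAP 9.1 fixes the column order as the three doses, then "placebo and overall subjects". The Safety Analysis Set (SAP 8.3) is everyone exposed to study drug, placebo included, so 'overall' combines drug and placebo.

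SAP 9.12.1 to 9.12.8 then specify counts and percentages of treatment-emergent adverse events (TEAEs), means and changes from Baseline, toxicity grades, ECG categories and listings. The one place that speaks of comparing, SAP 9.12.7, sets the extended follow-up against the data through Day 42, not dose against placebo. Protocol 15.1 and 15.6.4 are descriptive in the same way.

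Two labelling rules apply to anything extra. SAP 9.12 says "All post hoc safety analyses will be identified as such", and SAP 1.1 says "Any analysis performed not prospectively defined in this document will be labeled as post hoc and exploratory".

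For ECGs, SAP 9.12.4 summarises the Hour 3 recording in the PK Analysis Set, which SAP 8.6 limits to moxidectin recipients with a quantifiable concentration.

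**The concern.** An objective to compare needs an estimate of the comparison. The SAP supplies one for efficacy: SAP 9.11.1 gives dose-minus-placebo differences with intervals, and SAP 9.11.4.1 gives dose-versus-dose intervals without p-values for a purely exploratory question. The primary safety objective gets neither. A report that follows the plan would set percentages from about 50 subjects per arm side by side, and any statement that a dose resembled placebo would carry no measure of how uncertain that is.

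The pooling is also the less useful one. The group that adds drug exposure is the roughly 150 moxidectin subjects, and the SAP does not name it.

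The ECG table is a sharper case of the same gap. ECG change is a primary safety endpoint (protocol 6.2.1). Hour 3 is the only scheduled post-dose ECG before Week 16, and protocol 5.3.2.1 puts the median time of peak concentration at 3 to 4 hours. Without placebo subjects, that table cannot serve the stated comparison.

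**Working it through.** **The plan's own figure.** The documents give no safety power or precision. The only stated figure is efficacy power of about 75% (SAP 4), with n = 50 per arm, 40% vs 70%, two-sided alpha 0.019, and a Z-test with pooled variance.

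- Standard error under the null: sqrt(2 × 0.55 × 0.45 / 50) = 0.0995. Under the alternative: sqrt((0.24 + 0.21) / 50) = 0.0949.
- Power = Φ((0.30 − 2.345 × 0.0995) / 0.0949) = 75.9%. It reproduces. SAP 4 says the sample size was chosen for the efficacy objective, so safety precision is whatever 50 per arm gives.

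**Precision of a safety difference.** The documents do not assume any TEAE rate for this trial, so 5% to 30% is my assumed range, equal in both groups. Half-width = 1.96 × sqrt(p(1 − p)(1/n1 + 1/n2)).

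| Assumed rate | One dose vs placebo (50 v 50) | All moxidectin vs placebo (150 v 50) |
|---|---|---|
| 5% | ±8.5 points | ±7.0 points |
| 10% | ±11.8 | ±9.6 |
| 20% | ±15.7 | ±12.8 |
| 30% | ±18.0 | ±14.7 |

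The standard error ratio is sqrt((1/150 + 1/50) / (2/50)) = 0.816, so pooling the doses shortens the interval by about 18% when rates are similar.

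**Worked examples (Newcombe 95% intervals, illustrative counts).**

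- 10/50 vs 10/50: difference 0, interval −15.7 to +15.7 points.
- 10/50 vs 5/50: +10.0 (−4.3 to 24.2).
- 30/150 vs 5/50: +10.0 (−2.7 to 19.1).
- No events in either group, as may happen for serious TEAEs: the Wilson upper limit for 0/n is 3.84/(n + 3.84), which is 7.1% for n = 50 and 2.5% for n = 150. One dose minus placebo is then −7.1 to +7.1, and all moxidectin minus placebo −7.1 to +2.5. The Wald interval, the default for proportions in SAP 9.1, would have zero width here.

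**What each pooled column shows.**

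- 20% in every dose and 10% on placebo: 'overall' reads (150 × 0.20 + 50 × 0.10)/200 = 17.5%, which is neither the drug rate nor the placebo rate.
- 30% at 32 mg only and 10% at the other two doses: all moxidectin reads (50 × 0.30 + 100 × 0.10)/150 = 16.7%. Pooling the doses also dilutes, so the by-dose columns must stay.

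**Hour 3 ECG.** Protocol 9.3.2 gives the 3-hour ECG to the PK subset, and protocol 9.4.8 and SAP 5.1 draw that subset from all four arms, about 20 each. SAP 8.6 then removes placebo from the set used for the table. SAP 6.3 describes the subset as moxidectin cohorts only, which does not match SAP 5.1 and needs reconciling.

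**The case against.** Descriptive safety reporting is ordinary in Phase 2, and the SAP follows the protocol. Protocol 15.1 restates the objective and then says safety will be described through the adverse event profile. The columns are randomised arms side by side with numerators and denominators, so any reader can derive a difference and an interval. The table specifications are in a separate document (SAP 1.1), where an all-moxidectin column might already exist. All of this stands, and it limits the point. It does not supply a planned estimate for an objective that both documents word as a comparison.

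Four stronger readings are tempting, and the documents do not support them.

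- *That the option of models or tests opens the door to hidden, data-driven testing.* No model, endpoint or trigger is named, and the choice would naturally follow sight of results. But the post hoc labelling rules in SAP 1.1 and 9.12 mean such a test could not be presented as planned.
- *That the trial set out to exclude a safety difference of some size.* No safety hypothesis, alpha or margin is stated.
- *That 'overall' will be taken as the drug effect.* No section uses it so, and the separate arms stand in the same table.
- *That rare events will be missed for want of a pooled column.* Seeing them depends on how many people are exposed. All are tabulated, and adverse events are listed in full (SAP 9.12.1.3).

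On the ECG, SAP 9.12.4 goes on to speak of subjects selected for the PK Analysis Set, so the authors may have meant the PK subset. The definition in SAP 8.6 still excludes placebo.

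**Conclusion.** The point holds as a mismatch between a primary objective and its analysis, present in both documents: no between-group safety estimate with uncertainty is pre-specified, no all-moxidectin group is named in the SAP, and the Hour 3 ECG table as defined lacks a comparator. The width of the intervals comes from 50 per arm and would not shrink with any reporting change, except by about 18% for the pooled contrast. What changes is that the uncertainty would be stated. The figures rest on assumed event rates of 5% to 30%, about 50 exposed per arm, and similar rates across doses where they are pooled. No efficacy conclusion is affected. This is a worthwhile, low-cost improvement and not an error that invalidates the plan.

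**What to change.** Make the changes in the SAP before the Day 42 blind break; SAP 1.1 allows documented amendments up to unblinding and lets the SAP supersede the protocol's statistical methods.

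1. In SAP 9.12.1.3, for a short fixed list (any TEAE, study drug-related TEAE, TEAE of Grade 3 or higher, serious TEAE), report the risk difference versus placebo with a Newcombe or Miettinen-Nurminen 95% interval for 8, 16 and 32 mg and for all moxidectin combined. Label these descriptive and unadjusted, without p-values. Do not extend the list by a rule based on observed frequency, since that would select contrasts on the data.
2. Add an all-moxidectin column to the safety tables beside 'overall', and keep the by-dose columns.
3. In SAP 9.12.4, summarise the Hour 3 ECG in all Safety Analysis Set subjects who had one, including placebo, and align SAP 6.3 with SAP 5.1 on who is in the PK subset.

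The sentence that permits post hoc models or tests can stay. The cost is SAP wording and a few table columns, with no new data. The drawback is a handful of wide, unadjusted intervals, about ±15.7 points for one dose versus placebo at an assumed 20% rate, which readers must not treat as tests.

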9.4.5 Electrocardiograms

Twelve-lead ECGs will be performed before blood collection after the subject has been supine for approximately 10 minutes. ECGs will be performed in triplicate at Baseline (before randomization). After IP administration, another ECG will be performed at 3 hours (± 30 minutes) for the subjects in the PK subset. At Week 16, ECGs will be performed for all subjects. Repeat measurements will be performed if there are any abnormalities observed or artifacts are present. All ECG recordings will be reviewed by the Investigator or nominee and retained in the subject's study records.

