9.4.6 Safety Laboratory Tests

Blood and urine specimens collected during the trial may contain harmful pathogens. All personnel involved in collecting and handling biological specimens should follow appropriate precautionary procedures for handling biohazardous materials as currently recommended by the relevant local or national authority(ies). The processing of all biological specimens will be in accordance with relevant institutional Standard Operating Procedures (SOPs). Refer to the SRM for detailed instructions on sample collection, handling, and shipping, when a central laboratory is used.

Blood samples for hematology and serum chemistry will be collected at Screening, Day 14, and Day 28. Subjects with clinically significant abnormalities should have a repeat sample within 3 days. If there are ongoing clinically significant laboratory abnormalities from Day 28, laboratory tests will also be performed at Week 16.

Samples will be collected for the laboratory tests shown in [Table 6](#).

Table 6 Laboratory Tests

| Hematology | Serum clinical chemistry |
|--|---|
| White blood cell count (WBC) with differential | Alanine aminotransferase (ALT) |
| Red blood cell count | Aspartate aminotransferase (AST) |
| Hemoglobin | Alkaline phosphatase (ALP) |
| Hematocrit | Direct and Total Bilirubin |
| Mean corpuscular hemoglobin | Creatinine |
| Mean cell hemoglobin concentration | Creatine Kinase |
| Mean cell volume | Electrolytes (Sodium, Potassium, Chloride, Bicarbonate) |
| Platelets | Gamma-glutamyl transferase (GGT) |
| | Lactate dehydrogenase (LDH) |
| | Urea |

Creatinine clearance should be calculated using the Cockcroft-Gault formula:

For male subjects:

$$\frac{(140 - \text{age}[\text{years}]) \times \text{weight} (\text{kg})}{0.814 \times \text{creatinine} (\mu\text{mol/L})}$$

For female subjects:

$$\frac{0.85 \times (140 - \text{age}[\text{years}]) \times \text{weight} (\text{kg})}{0.814 \times \text{creatinine} (\mu\text{mol/L})}$$

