12.5.5 Clinical Laboratory Abnormalities and Other Abnormal Assessments

All laboratory values must be reviewed by the Investigator or medically qualified designee as soon as practical after the data are available.

Any laboratory values outside the reference range will be evaluated for clinical significance. Abnormal laboratory values should be graded for severity using the FDA Guidance for Industry: Toxicity Grading Scale for Healthy Adult and Adolescent volunteers Enrolled in Preventive Vaccine Clinical Trials in [Appendix 1](#). Where parameters are not addressed within this Toxicity Grading Scale, laboratory abnormalities should be assessed as "Clinically Significant" or "Not Clinically Significant". Laboratory abnormalities that occur without related clinical symptoms and signs should generally not be recorded as AEs unless they represent a clinically significant event. Where possible, the overall diagnosis rather than the laboratory abnormality should be

recorded on the AE CRF. This will avoid duplication of laboratory abnormalities in both the AE and laboratory reports. Abnormal laboratory results that are of clinical significance should be reviewed by the Medical Monitor.

All abnormal clinically significant values should be confirmed by repeat testing as soon as possible, preferably within 3 calendar days of receipt of results and prior to dose interruption or discontinuation, unless such a delay is not consistent with good medical practice.

For the purpose of monitoring and managing abnormalities, the Baseline value is defined as the last value prior to the administration of the first dose of IP.

Any laboratory test result that meets the criteria for a SAE will be reported as per Section 12.3.3.

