9.12.3 Clinical Laboratory Assessments

All laboratory values (hematology and serum chemistry) will be converted to the International System of Units (SI) for the purposes of summary and listing.

Hematology and serum chemistry data will be listed separately including change from Baseline and flagging all out-of-range values. Toxicity grades will be derived where possible for each hematology and biochemistry result as described in Appendix 1 of the current protocol (The 2007 FDA Guidance for Industry: Toxicity Grading Scale for Healthy Adult and Adolescent volunteers Enrolled in Preventive Vaccine Clinical Trials). Those grades will be included in the listings.

Aggregate summary data for hematology and serum chemistry test results will be provided for Baseline and post-Baseline assessments. These analyses will include changes from Baseline, to be presented only for subjects with non-missing assessments at both timepoints. Means, medians, SDs, minimum, and maximum values will be provided for both test results and for the individual change from Baseline.

A summary tabulation will show the number and proportion of subjects for the serum and hematology laboratory abnormalities graded using the scales shown in Appendix 1 of the current protocol.

9.12.4 12-Lead ECGs

An overall summary table will be provided for normal and abnormal 12-lead ECGs in the SfAS and in the PK Analysis set for the Hour 3 ECG. Abnormal 12-lead ECGs will be summarized by treatment group and overall and by whether they were normal/abnormal and if abnormal, clinically significant or not significant. ECG data are collected at Baseline and Week 16 only for subjects not selected for the PK Analysis set.

All 12-lead ECG data will be listed.

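### The last-value rule in SAP 9.12 can let a normal repeat replace a transient abnormal ECG or laboratory value; the abnormality tables need a written worst-value rule

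*SAP*

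**What the plan says.** SAP 9.12 opens with rules for all safety data. Where several values exist, "If multiple measurements within a time interval were taken, the last value taken within that time interval will be used." The worst value is only a fallback: "If the last value within the time interval cannot be determined, the worst value within the time interval will be used." Nothing is deleted: "All recorded values, including repeated measurements, will be included in listings," with out-of-range values flagged. The section does not define 'time interval'.

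The protocol decides when extra values arise. For ECGs (9.4.5): "Repeat measurements will be performed if there are any abnormalities observed or artifacts are present." For laboratory tests (9.4.6): "Subjects with clinically significant abnormalities should have a repeat sample within 3 days." Section 12.5.5 counts the time from a different point: "All abnormal clinically significant values should be confirmed by repeat testing as soon as possible, preferably within 3 calendar days of receipt of results."

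Two tables are affected. SAP 9.12.3 plans a laboratory table: "A summary tabulation will show the number and proportion of subjects for the serum and hematology laboratory abnormalities graded" on the scales in Protocol Appendix 1. It also derives a grade for each individual result and puts those grades in the listings, but it does not say which value the subject table counts. SAP 9.12.4 classes ECGs as normal or abnormal, and abnormal ones as clinically significant or not. ECGs are not graded.

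On adverse events, Protocol 12.5.5 says: "Laboratory abnormalities that occur without related clinical symptoms and signs should generally not be recorded as AEs." The same sentence goes on to make an exception for clinically significant events.

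**The concern.** An abnormal value is what prompts the second measurement. A rule that keeps the last value therefore tends to swap the abnormal reading for its repeat. If the abnormality was short-lived, the table shows a normal subject.

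Changes in ECGs and laboratory parameters are primary safety endpoints (Protocol 6.2.1), and post-dose sampling is thin. Laboratory tests are scheduled for everyone only at Days 14 and 28. Scheduled post-dose ECGs are Hour 3 in the PK subset (about 20 subjects per arm) and Week 16. Hour 3 is also the median time of peak concentration reported for scabies patients in Protocol 5.4.3, so it is the tracing most likely to show an acute effect.

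The rule is also out of step with how the SAP treats adverse events. SAP 9.12.1.1 takes the highest severity per subject, sets a missing severity to Grade 3 and sets a missing relationship to definite.

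**Working it through.** The plan states no abnormality, repeat or persistence rate, so there is no figure to reproduce. The check is a reading of the text plus an illustration.

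**1. Which rule governs the tables?** Sections 9.12.3 and 9.12.4 sit under 9.12 and contain no worst-value or any-occurrence instruction. For ECGs the general rule therefore applies on a plain reading. For graded laboratory results there are two readings. Either the general rule applies, or the table counts any subject with a graded result, which the result-by-result grading in 9.12.3 would allow.

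**2. Does the repeat fall in the same interval?** Suppose the interval is the visit window in Protocol 9.2 or Table 1.
- Hour 3 ECG: a repeat of an abnormal tracing would naturally be taken at the same visit, so it shares the interval.
- Day 28 laboratory (−2/+4 days): a sample on Day 28 repeated 3 days later falls on Day 31, inside the window that ends on Day 32.
- Day 14 laboratory (±2 days): a sample on Day 14 repeated 3 days later falls on Day 17, outside the window that ends on Day 16. The first value would then stand.
- If the 3 days run from receipt of results (Protocol 12.5.5), repeats fall later still.

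**3. Size.** Let n be subjects per arm, a the share with an abnormal first value at a visit, q the share of those with a repeat in the same interval, and r the probability that the repeat is still abnormal.
- Count by worst or any value: n·a
- Count by last value: n·a·(1 − q(1 − r))
- Relative loss: q(1 − r)

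With n = 50 (SAP section 4) and a = 10% (assumed), the worst-value count is 50 × 0.10 = 5.0. Expected last-value counts, with q and r also assumed, are:

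| q | r | Last-value count | Loss |
|---|---|---|---|
| 0 | any | 5.0 | 0% |
| any | 1 | 5.0 | 0% |
| 0.25 | 0.8 | 5 × (1 − 0.05) = 4.75 | 5% |
| 0.5 | 0.5 | 5 × (1 − 0.25) = 3.75 | 25% |
| 1 | 0.5 | 5 × (1 − 0.50) = 2.5 | 50% |
| 1 | 0.3 | 5 × (1 − 0.70) = 1.5 | 70% |

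For the Hour 3 ECG, with about 20 subjects per arm, one lost subject is 1/20 = 5 percentage points.

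**4. Direction.** For a count of subjects with any abnormality at a visit, a repeat prompted by an abnormal value can only keep or remove the subject. For the grade itself, a repeat can be worse, and the last-value rule then raises it.

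**5. Contrast between arms.** If q and r are the same in every arm, each proportion is multiplied by 1 − q(1 − r). The risk difference shrinks by that factor and the ratio does not change.

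**The case against.** A reader might infer that graded laboratory abnormalities are systematically under-counted, that they vanish from every summary, and that the dose-versus-placebo comparison is biased toward no difference. The documents do not support that much, for these reasons.

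- **The graded table's counting rule is not stated.** If it counts any graded result, the laboratory loss is zero. SAP 1.1 leaves table specifications to a separate document.
- **Laboratory repeats are required only for clinically significant values.** Many graded values need not qualify; Grade 1 in Appendix 1 includes sodium of 144 to 145 mEq/L. With no repeat there is nothing to replace. The values that are repeated are largely those that the exception in Protocol 12.5.5 allows to be recorded as adverse events.
- **The interval is undefined,** and a Day 14 repeat may fall outside the visit window.
- **Replacement can be right.** An ECG repeated for an artifact should supersede the first tracing.
- **Nothing is lost from the data,** and the safety analysis is descriptive.

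All of this stands, and it limits the point. It does not remove it. The ECG table has no competing reading, and any ECG abnormality prompts a repeat. Listings do not give a comparison by arm, and recovery through adverse events is partial. Equal treatment of the arms does not by itself protect the risk difference (step 5), but a distorted contrast needs rates that the documents do not give. An ambiguous counting rule and an undefined interval are themselves reasons to add the missing sentences.

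**Conclusion.** The point holds in a limited form. As written, SAP 9.12 allows a transient abnormal value to be replaced by its normal repeat in the abnormal-ECG table, with Hour 3 in the PK subset the clearest case. It does the same in the graded-laboratory table if the general rule governs that table. Such a value remains in the listings and, where clinically significant, possibly in the adverse event tables.

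The relative under-count is q(1 − r). It runs from 5% to 70% over the assumed grid of q from 0.25 to 1 and r from 0.3 to 0.8. It is zero if no repeat in the same interval normalises. None of these rates is in the documents, so the actual size cannot be derived, and neither systematic under-counting nor a biased treatment comparison has been shown. This is a cheap improvement to make before unblinding.

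**What to change.** Amend SAP 9.12, 9.12.3 and 9.12.4 before the blind is broken for the Day 42 analysis:

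- Define 'time interval' for laboratory, ECG and vital-sign values, and say where repeat and unscheduled values fall.
- State that the toxicity-grade table and the abnormal-ECG table count each subject's worst valid post-Baseline value, including repeat and unscheduled values and excluding tracings rejected for artifact.
- Keep one pre-specified value for by-visit means and changes from Baseline. The existing last-value rule is acceptable there.
- State how the triplicate Baseline ECG (Protocol 9.4.5) is classified. At present the Baseline definition in SAP section 7 points to the last non-missing assessment.

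The cost is SAP wording and minor programming, with no new data collection. The abnormality tables will look slightly less favourable in every arm.
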